## 3. OBJECTIVES AND ENDPOINTS

## PART-1: SAD

| Objectives   | Endpoints   |  |  |
|--|---|--|--|
| Primary:   | Primary:  |  |  |
| To assess the safety and tolerability following a single dose of PF-07321332 alone or in combination with a PK boosting agent (ritonavir).                               | 
 
Frequency, severity, and causal relationship of TEAEs and withdrawals due to TEAEs.
 
Frequency and magnitude of abnormal laboratory findings.
 
Changes from baseline in vital sign measurements and 12-lead ECG parameters.
 
                   |  |  |
| Secondary:   | Secondary:  |  |  |
| To assess the plasma PK profile of
PF-07321332 following single ascending
doses of PF-07321332 alone or in
combination with a PK boosting agent
(ritonavir). | 
 
Plasma PK parameters of PF-07321332:
 
Cmax, Tmax, AUClast, Cmax(dn), AUClast(dn).
 
If data permit, AUCinf, AUCinf(dn), t½, Vz/F, and CL/F.
 
 |  |  |
| Tertiary/Exploratory:  | Tertiary/Exploratory:   |  |  |
| To explore metabolites in plasma, urine, and feces, if data permit.  | Qualitative characterization of metabolites of PF-07321332 in pooled plasma, urine, and feces if data permit.   |  |  |
| Quantitative excretion of drug-related
material using  F-NMR spectroscopy, if
data permit.  | Total excretion of drug-related material in urine and feces separately, and both routes combined, expressed as a percent of total dose administered, if data permit.  |  |  |
| To determine the oral bioavailability of a tablet formulation of PF-07321332 relative to suspension, if evaluated (Optional).  | The ratio of AUC last , AUC inf and C max of tablet formulation and suspension.  |  |  |
| To evaluate the effect of food (high fat meal) on the exposure of PF-07321332 following a single oral dose of PF-07321332 tablet formulation, if evaluated (Optional).   | The ratio of AUC last , AUC inf and C max under fed condition and fasted condition.  |  |  |

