| Cohort 2 | N=2 | PL           | D4       | D6                    | PL+Food                  |
|          | N=2 | D2           | PL       | D6                    | D2+Food b     |
|          | N=2 | D2           | D4       | PL                    | D2+Food b     |

Dose levels D1 to D6 are specified in Table 9.

- a. Period 3 and 4 are optional. These periods may be used for evaluation of additional dose levels or combination with ritonavir or relative bioavailability of tablet formulation or food effect etc.
- b. Period and dose levels for relative bioavailability of tablet or administration with food may be changed based on emerging PK data. If relative bioavailability and food effect conducted in Period 3 or 4, the active/Placebo allocation will be the same as equivalent dose used in period 1 or 2.

There will be a washout interval of  $\geq 5$  days between dosing to a given participant. Participants will be required to stay at the CRU for the duration of the washout interval. However, they may be released at the discretion of the investigator. The washout interval may be adjusted based on data emerging from previous cohorts/periods.

Optional Period 3 or 4 of Cohort 1 or 2 may be used to explore food effect (high-fat high-calorie meal) and/or relative bioavailability. If conducted, the active/Placebo allocation will be the same as equivalent dose used in Period 1 or 2.

At dose level of D3 (Cohort-1, Period 2), the urine and feces will be collected for 5 days as specified in SoA for F-NMR spectroscopy and metabolite profiling. Based on the emerging PK data, the dose level for urine and feces collection may be changed. If needed, the feces and urine may also be collected at an additional dose level.

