## 6.1. Study Intervention(s) Administered

PF-07321332 and placebo will be provided by Pfizer as bulk powders for extemporaneous preparation of oral suspensions at the CRU.

PF-07321332 or placebo will be presented to the participants in individual dosing containers.

In addition, PF-07321332 and matching placebo may also be supplied as tablets. If provided, tablets will be supplied to the CRU in bulk along with individual dosing containers for unit dosing.

Ritonavir 100 mg tablets will be supplied locally by the CRU.

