# 9.4.3.2. Statistical Methods for PK Data

No formal inferential statistics will be applied to the plasma PK data apart from the comparisons of formulation and food effect in either Part 1 or Part 3.

For all parts of the study, plasma concentrations will be listed and summarized descriptively by PK sampling time and treatment. Individual participant and median profiles of the concentration-time data will be plotted by treatment. For summary statistics and median plots by sampling time, the nominal PK sampling time will be used, for individual participant plots by time, the actual PK sampling time will be used for plasma samples. Median profiles will be presented on both linear-linear and log-linear scales.

The plasma PK parameters listed in Table 12 and Table 13 will be summarized descriptively by dose.

For PART-1,PART-2 and PART-5, dose normalized (to 1 mg) AUCinf or AUCtau and Cmax of PF-07321332 will be plotted against dose (using a logarithmic scale) and will include individual participant values as well as the geometric means for each dose. These plots may be used to help understand the relationship between the PK parameters and dose.

For PART-2, urine amounts as listed in Table 13 of PF-07321332 will be listed and summarized descriptively, if data permit.

For PART-3, natural log transformed AUClast, Cmax, and AUCinf (if data permit) for PF-07321332 will be analyzed using a mixed effect model with sequence, period, and treatment included as fixed effects and participant nested within sequence as a random effect. Estimates of the adjusted mean differences (Test-Reference) and corresponding 90% CIs will be obtained from the model. The adjusted mean differences and 90% CIs for the differences will be exponentiated to provide estimates of the ratio of adjusted geometric means (Test/Reference) and 90% CIs for the ratios.

The following comparisons will be made:

| Comparison | Test  | Reference  |
|------------|---|--|
|            | PF-07321332 tablet formulation in fasted state (B)              | PF-07321332 oral suspension in fasted state (A)    |
|            | PF-07321332 tablet formulation in fed (high fat meal) state (C) | PF-07321332 tablet formulation in fasted state (B) |

Additional specifications about the tables, listings, and figures will be outlined in the SAP.

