2.1. Study Objectives, Endpoints, and Estimands

There are no estimands for this study.

PART-1: SAD

Objectives	Estimands	Endpoints
Primary:	Primary:	Primary:

 To assess the safety and tolerability following a single dose of PF-07321332 alone or in combination with a PK boosting agent (ritonavir). 	N/A	
 Frequency, severity, and causal relationship of TEAEs and withdrawals due to TEAEs. Frequency and magnitude of abnormal laboratory findings. Changes from baseline in vital sign measurements and 12-lead ECG parameters.
Secondary:	Secondary:	Secondary:

 To assess the plasma PK profile of PF-07321332 following single ascending doses of PF-07321332 alone or in combination with a PK boosting agent (ritonavir) 	N/A	
 Plasma PK parameters of PF-07321332: 
 C_{max}, T_{max}, AUC_{last}, C_{max(dn)}, AUC_{last(dn)}. If data permits, AUC_{inf}, AUC_{inf(dn)}, t_{1/2}, V_{z/F}, and CL/F.
Tertiary/Exploratory:	Tertiary/Exploratory:	Tertiary/Exploratory:

 To explore metabolites in plasma, urine, and feces, if data permits. 	N/A	
 Qualitative characterization of metabolites of PF-07321332 in pooled plasma, urine, and feces as data permits.

 Quantitative excretion of drug-related material using ¹⁹F-NMR spectroscopy, if data permits. 	N/A	
 Total excretion of drug-related material in urine and feces separately, and both routes combined, expressed as a percent of total dose administered, if data permits.

 To determine the oral bioavailability of a tablet formulation of PF-07321332 relative to suspension, if evaluated (Optional) 	N/A	
 The ratio of AUC_{last}, AUC_{inf} and C_{max} of tablet formulation and suspension.

 To evaluate the effect of food (high fat meal) on the exposure of PF-07321332 following a single oral dose of PF-07321332 tablet formulation, if evaluated (Optional) 	N/A	
 The ratio of AUC_{last}, AUC_{inf} and C_{max} of tablet formulation under fed condition and fasted condition.

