To assess any effect of food/formulation in **PART-3**, natural log transformed AUC_{last} , C_{max} , and AUC_{inf} (if data permit) for PF-07321332 will be analyzed using a mixed effects model with sequence, period and treatment included as a fixed effect and participant nested within sequence as a random effect. If performed, to assess any effect of food/formulation in **PART-1**, natural log transformed AUC_{last} , C_{max} , and AUC_{inf} (if data permit) for PF-07321332 will be analyzed using a mixed effects model with treatment as a fixed effect and participant as a random effect using participants with data from both periods only. The Kenward-Roger adjustment for the degrees of freedom will be used. Estimates of the adjusted mean differences (Test-Reference) and corresponding 90% CIs will be obtained from the model. The adjusted mean differences and 90% CIs for these differences will be exponentiated to provide estimates of the ratio of adjusted geometric means (Test/Reference) and 90% CIs for these ratios.

[figure not shown]
The following comparisons will be made:

Comparison	Test	Reference
Formulation	PF-07321332 tablet formulation in fasted state (B)	PF-07321332 oral suspension in fasted state (A)

Food Effect	PF-07321332 tablet formulation in fed (high fat meal) state (C)	PF-07321332 tablet formulation in fasted state (B)
-------------	---	--

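### Does the single comparison list in SAP 6.2 leave the optional PART-1 food effect without an estimable contrast?

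*SAP*

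**What the plan says.** SAP 6.2 gives two models for the effect of food or formulation. For PART-3, sequence, period and treatment are fixed effects and participant within sequence is random. For PART-1, if the comparison is performed, treatment is fixed, with "participant as a random effect using participants with data from both periods only". Shared text on Kenward-Roger degrees of freedom and 90% confidence intervals follows, and then one comparison table. Its formulation row is B vs A. Its food row tests "PF-07321332 tablet formulation in fed (high fat meal) state (C") against the tablet fasted (B).

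Protocol 9.4.3.2 prints the same pairs, but only after the PART-3 model, in which the PK parameters "will be analyzed using a mixed effect model with sequence, period, and treatment included as fixed effects". It gives no PART-1 model, although it allows inferential formulation and food comparisons in either part. The letters A, B and C are defined in Protocol 4.1, Table 7, as the PART-3 treatments.

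The PART-1 food endpoint reads "of tablet formulation under fed condition and fasted condition" in SAP 2.1 and only "under fed condition and fasted condition" in the endpoint cell of Protocol 3. The protocol objective beside that cell names the tablet. Both documents list the endpoint as optional and exploratory.

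The provisional PART-1 scheme in Protocol 4.1, Table 6, places D3 as tablet in Cohort 1, Period 4, and D2 with food in Cohort 2, Period 4. Footnote b adds "Period and dose levels for relative bioavailability of tablet or administration with food may be changed based on emerging PK data" and says that, if these comparisons are run in Period 3 or 4, "the active/Placebo allocation will be the same as equivalent dose used in period 1 or 2".

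**The concern.** The SAP put a PART-1 model ahead of a list that the protocol attaches to PART-3 alone, and did not adapt the list. Taken at face value, the PART-1 food contrast is then tablet fed versus tablet fasted, which nobody receives under the printed scheme, while the fed and fasted pair that the scheme provides has no row. The term for both periods is also undefined in a cohort with up to four.

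Two consequences would matter. The only inferential PK analysis open to PART-1 might have no contrast fixed in advance. A food effect measured on the suspension might also be reported as a tablet effect: the product is supplied by default as "bulk powders for extemporaneous preparation of oral suspensions at the CRU", and Table 6 does not mark the D2 fed dose as tablet.

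**Working it through.** **Inputs.** Protocol 4.1, Table 6, has six sequence rows of 2 participants each, Periods 1 to 4 in order (PL = placebo):

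| Cohort | Row | P1 | P2 | P3 | P4 |
|---|---|---|---|---|---|
| 1 | 1 | PL | D3 | D5 | D3 tablet |
| 1 | 2 | D1 | PL | D5 | PL |
| 1 | 3 | D1 | D3 | PL | D3 tablet |
| 2 | 1 | PL | D4 | D6 | PL, fed |
| 2 | 2 | D2 | PL | D6 | D2, fed |
| 2 | 3 | D2 | D4 | PL | D2, fed |

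**The plan's own allocation.** Protocol 9.2.1 gives 4 active and 2 placebo per dose level. Each of the 8 cohort-periods has two active rows (2 × 2 = 4) and one placebo row (2). The figure is reproduced.

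**Pairs within a participant.**
- B vs A, tablet fasted against suspension fasted at D3: Cohort 1, rows 1 and 3, 2 + 2 = 4 pairs, Period 2 then Period 4.
- C vs B, tablet fed against tablet fasted: no Cohort 1 row has a fed dose and no Cohort 2 row has a fasted tablet dose, so 0 of 12. This holds whether the D2 fed dose is suspension or tablet.
- D2 fed against D2 fasted: Cohort 2, rows 2 and 3, 2 + 2 = 4 pairs, Period 1 then Period 4. This pair is in neither listed row.

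**Is the empty row fixed by the plan?** No. Protocol 4.1 lets the optional Period 3 or 4 of either cohort explore food, relative bioavailability or both, and lets PART-1 treatment sequences be adjusted. As an example, suppose Cohort 1 has D3 suspension in Period 2, D3 tablet fasted in Period 3 and D3 tablet fed in Period 4. Footnote b keeps the active allocation, so the same 4 participants receive A, B and C, and both listed rows have 4 pairs.

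**Does the PART-1 model need a period term?** Under the printed scheme all 4 food pairs run in one order. A design matrix with intercept, treatment, period and 3 participant terms has 6 columns and rank 5, so treatment and period cannot be separated. Leaving period out is forced by the design.

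**What could PART-1 add?** Take the layout of Protocol Table 11: the 90% interval half-width on the log scale, at its 80% coverage bound, is

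h = t(0.95, df) × SD × √(2/n) × √(χ²(0.80, df)/df).

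- PART-3, n = 18, SD = 0.3, df = 2n − 4 = 32: 1.694 × 0.100 × √(38.47/32) = 0.186. For a ratio of 1.0 the interval is 0.83 to 1.20, which matches Table 11.
- PART-1, n = 4 pairs, df = 3, same SD: 2.353 × 0.212 × √(4.642/3) = 0.621, or 0.54 to 1.86.
- With SD = 0.2, the intervals are 0.88 to 1.13 for PART-3 (again matching Table 11) and 0.66 to 1.51 for PART-1.

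The two SDs are the ones Table 11 uses; applying them to PART-1 is an assumption.

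**The case for a change.** The strongest case for a change is that either reading leaves something unsaid. If the list covers PART-1, its food row is empty under the printed scheme. If it does not, PART-1 has a model with no named contrast. In both cases the D2 fed and fasted pair, which footnote b protects through the allocation, appears nowhere. SAP version 2.0 is dated 25 August 2021, and Protocol 4.2, in the PART-5 rationale, already describes SAD exposure in the past tense, so the arms dosed could perhaps have been named.

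The gap in wording is real, and so is the count of zero. The harm is not established. The two feared outcomes exclude each other: following the list literally yields no estimate, while analysing the D2 pair means departing from the list, and nothing then requires a tablet label, since SAP 5.2 presents results by treatment. Confounding of food with formulation would need the D2 fed dose to be tablet and D2 to be suspension. Table 6 marks the tablet where it means tablet and does not do so here. The added words in SAP 2.1 bring the endpoint into line with the protocol's own objective. The mismatch that remains is between that objective and a scheme labelled provisional. In a two-treatment paired model, both periods can sensibly mean only the test period and its reference period. The past-tense remark concerns dose proportionality and does not show which optional arms were run.

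**Conclusion.** No change is needed. The SAP is silent on which part its list serves, and an analyst can fill that gap from the documents. The A, B and C codes belong to PART-3. A PART-1 comparison, if run, pairs the test period with the same-dose reference period in the same participants, and the formulation given is known from the dosing record.

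Under the provisional scheme the size is 0 pairs for the listed food row, 4 for the unlisted D2 food pair and 4 for the formulation row. The zero depends on two things: reading the list as covering PART-1, and the printed scheme being run unaltered. The protocol fixes neither. No primary or secondary endpoint is touched, and the tablet food effect comes from PART-3, with period in the model and up to 18 participants. A PART-1 ratio from 4 fixed-order pairs would be too imprecise to alter that answer under the SDs of 0.2 and 0.3 assumed above. Naming the PART-1 pairs would tidy the text and would not alter a conclusion of the study.

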6.3. Other Endpoints

CCI

Qualitative characterization of metabolites of PF-07321332, quantitative excretion of drug related material using ^{19}F -NMR spectroscopy, metabolic profiling/identification and determination of relative abundance of PF-07321332 and its metabolites will be analysed separately and maybe included in the CSR in an appendix. Exploring of PK by microsampling is an exploratory endpoint and will not be included in the CSR.

6.4. Subset Analyses

No subset analyses will be performed.

6.5. Baseline and Other Summaries and Analyses

6.5.1. Study Conduct and Participant Disposition

Participant evaluation groups will show participant disposition by treatment. Frequency counts and percentages will be supplied for participant discontinuation(s) by treatment. Data will be reported in accordance with the sponsor reporting standards.

6.5.2. Demographic Data

Demographic data (age, biological sex, race, ethnicity, weight, body mass index and height) will be summarised by cohort for PART-1, PART-3 and PART-5, by treatment for PART-2 and PART-4, and overall (if applicable) in accordance with the sponsor reporting standards.

6.5.3. Concomitant Medications and Nondrug Treatments

All concomitant medication(s) as well as non-drug treatment(s) will be reported according to current sponsor reporting standards.

6.5.4. Other Screening Data

These data will not be recorded in the study database, and therefore will not be listed.

6.6. Safety Summaries and Analyses

In all 5 parts of the study, all safety analyses will be performed on the Safety Analysis Set.

6.6.1. Adverse Events

Adverse events will be reported in accordance with the sponsor reporting standards.

6.6.2. Laboratory Data

Laboratory data will be listed and summarized by treatment in accordance with the sponsor reporting standards. Baseline is as defined in Section 3.5.2.

6.6.3. Vital Signs

Absolute values and changes from baseline in supine systolic and diastolic blood pressure, pulse rate, temperature and respiratory rate will be summarized by treatment and time post-dose, according to sponsor reporting standards. Tables will be paged by parameter. Baseline is as defined in Section 3.5.3.

Mean changes from baseline for supine systolic and diastolic blood pressure, pulse rate, temperature and respiratory rate will be plotted against time post-dose. Each part will have its own output with 1 line for each treatment. Placebo will be pooled in the plots for PART-1, PART-2 and PART-5, although the Japanese placebo in PART-2 will be treated as a separate treatment. Corresponding individual plots of changes from baseline will also be produced for each treatment.

Maximum decrease from baseline for supine systolic and diastolic blood pressures and respiratory rate and maximum increase from baseline for supine pulse rate and temperature will be summarized by treatment, according to sponsor reporting standards.

Minimum and/or maximum absolute values and changes from baseline for supine vital signs will also be summarized descriptively by treatment using categories as defined in [Appendix 1](#). Numbers and percentages of participants meeting the categorical criteria will be provided. All planned and unplanned post-dose time points will be counted in these categorical summaries.

6.6.4. ECG

Absolute values and changes from baseline in QT, heart rate, QTcF, PR and QRS will be summarized by treatment and time post-dose using sponsor reporting standards. Tables will be paged by parameter. Baseline is as defined in [Section 3.5.4](#).

Mean changes from baseline in QT, heart rate and QTcF will be plotted against time postdose. Each part will have its own output with 1 line for each treatment. Placebo will be pooled in the plots for PART-1, PART-2 and PART-5, although the Japanese placebo in PART-2 will be treated as a separate treatment. Corresponding individual plots of changes from baseline will also be produced for each treatment.

Changes from baseline in QTcF will also be plotted separately against drug concentrations of PF-07321332. This will be a scatter plot for all observations where QTcF and drug concentration are recorded. Placebo data will also be included (with drug concentration set to zero). Different symbols will be used for each treatment.

Maximum increase from baseline for QTcF will be summarized by treatment, according to sponsor reporting standards.

ECG endpoints and changes from baseline (QTcF, PR and QRS) will also be summarized descriptively by treatment using categories as defined in Appendix 1 (for QTcF these correspond to the Pfizer Guidance in Section 8). Numbers and percentages of participants meeting the categorical criteria will be provided. All planned and unplanned postdose time points will be counted in these categorical summaries.

Listings of participants with any single post-dose value >500 msec will also be produced for QTcF.

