#### 1.2. Schema

Figure 1. C4671001 Study Design

\*Optional dose levels in SAD/MAD may be used to explore higher doses or food effect or relative bioavailability or in combination with ritonavir (see more details in Section 4.1). Dosing with food may be done in one or more cohorts in SAD/MAD based on the emerging PK/safety data. PART-4: Metabolism and Excretion (M&E) is an open-label single dose cohort (see more details in Section 4.1). PART-5: supratherapeutic exposure (SE) is a double-blind, sponsor-open, randomized, cross-over cohort (See more details in Section 4.1).

SAD dose levels D1 to D8 and MAD dosing regimens DR1 to DR4 are listed in Table 9 and Table 10, respectively in Section 4.3.

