## PART-1: SAD

SAD will include 2 interleaving cohorts with a total of approximately 12 participants planned (approximately 6 participants in each cohort), with 4-period cross-over in each cohort. Period 3 and 4 are optional periods which may be used to further explore PK at additional doses or PK in combination with ritonavir or relative bioavailability of a new formulation or food effect (high-fat high-calorie meal), etc, based on emerging safety, tolerability and PK assessments. For each period, approximately 4 participants will receive a single oral dose of PF-07321332, and approximately 2 participants will receive placebo after at least 10 hours of fasting. In order to improve gastrointestinal tolerability, if required based on emerging safety data, PF-07321332 may also be dosed with standard meal (Section 5.3.1). If required to be dosed in fed state, the participants will be required to eat a meal before drug administration as specified in Sections 5.3.1 and 6.1. Each participant may receive either a single dose of PF-07321332 or a placebo during each period. In each period, participants on active treatment in Cohort 1 will receive D1, D3, D5 and D7 dose levels and Cohort 2 will receive D2, D4, D6 and D8 dose levels in dose escalation format as specified in Table 9 (Section 4.3). Provisional dosing scheme in PART-1 is provided in Table 6. In SAD cohorts requiring co-administration of PF-07321332/placebo with ritonavir, all participants (active and placebo) will receive 3 doses of 100 mg of ritonavir as specified in the SoA. Except D1 of Cohort 1 in SAD, all other dose levels and/or meal condition may be changed based on emerging PK and safety data. Dose escalation to subsequent dose levels in SAD cohorts will be based on all available (a minimum of 48 hours post-dose) safety data and PK over approximately >6 hours in a minimum of 4 participants (3 active and 1 placebo) at previous dose levels.

Table 6. Provisional Dosing Scheme in Part-1:SAD

|          |     | Period 1     | Period 2 | Period 3 a | Period 4 a    |
|----------|-----|--------------|----------|-----------------------|--------------------------|
| Cohort 1 | N=2 | Placebo (PL) | D3       | D5                    | D3 (Tablet) b |
|          | N=2 | D1           | PL       | D5                    | PL                       |
|          | N=2 | D1           | D3       | PL                    | D3 (Tablet) b |

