5. GENERAL METHODOLOGY AND CONVENTIONS

5.1. Hypotheses and Decision Rules

There is no statistical hypothesis testing planned for this study and no statistical decision rules will be applied.

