5.2. General Methods

Unless otherwise stated, all summaries and plots will be presented by treatment.

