6. ANALYSES AND SUMMARIES

Separate tables will be produced for **PART-1: SAD**, **PART-2: MAD**, **PART-3: Relative Bioavailability/Food Effect Cohort**, **PART-4: Metabolism and Excretion Cohort** and **PART-5: Supratherapeutic Exposure Cohort**, unless otherwise specified. Placebo and Placebo + Ritonavir will be separate treatment groups. In Part-2, Japanese and non-Japanese will be separate treatment groups.

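### Does pooling placebo in the vital-sign and ECG plots, without mentioning ritonavir, call for a change to the SAP?

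*SAP*

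**What the plan says.** SAP Section 6 fixes the groups: "Placebo and Placebo + Ritonavir will be separate treatment groups". It also separates Japanese from non-Japanese participants in PART-2. SAP 5.2 sets the default for outputs: "Unless otherwise stated, all summaries and plots will be presented by treatment".

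For the mean plots, SAP 6.6.4 asks for this layout: "Each part will have its own output with 1 line for each treatment". It then adds "Placebo will be pooled in the plots for PART-1, PART-2 and PART-5", with one exception: "although the Japanese placebo in PART-2 will be treated as a separate treatment". SAP 6.6.3 uses the same wording for vital signs. Neither section mentions ritonavir.

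In the protocol, ritonavir in PART-1 and PART-2 is conditional. The footnote to the schema says "Optional dose levels in SAD/MAD may be used to explore higher doses or food effect or relative bioavailability or in combination with ritonavir", and the PART-1 design text says "Period 3 and 4 are optional periods which may be used to further explore PK at additional doses or PK in combination with ritonavir". Where a cohort needs co-administration, placebo participants take ritonavir as well. In PART-5 all participants take it in every period.

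**The concern.** Section 6 makes two separations, but the plot text repeats only the Japanese one. Read literally, the pooling sentence would put boosted and unboosted placebo on one line wherever a part contains both. Giving ritonavir to placebo participants in boosted cohorts creates a comparator that isolates PF-07321332. A mixed line would remove that comparator from the figure, and it would match neither placebo group in the tables. Changes from baseline in vital signs and ECG are primary endpoints in PART-1 and PART-2, so a reader could credit part of a ritonavir effect to the study drug.

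**Working it through.** **Which reading fits the text.**

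- *Within ritonavir status.* Pooling runs over cohorts and periods inside each Section 6 group. PART-5 must work this way, since all its placebo is boosted. On this reading there is no conflict.
- *Across ritonavir status.* SAP 5.2 lets a section depart from the by-treatment default if it says so, and 6.6.3 and 6.6.4 do say so for named parts. The Japanese exception would be redundant if Section 6 still governed, so the wording leans this way. On this reading pooling is a declared choice of presentation, not a contradiction.

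**What a mixed line would carry.** Let D be the drug effect, R the post-baseline ritonavir effect and f the boosted share of placebo records.

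- Boosted active minus pooled placebo = (D + R) − fR = D + (1 − f)R.
- Unboosted active minus pooled placebo = D − fR.

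Inputs: about 2 placebo records per cohort-period in PART-1 (protocol Table 6, provisional dosing scheme) and about 2 per cohort in PART-2 (protocol 4.1). With k of n cells boosted, f = k/n. The documents do not fix k, so k is an assumption. The ranges below confine ritonavir to the optional periods and to optional Cohorts 5 and 6.

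| Part and layout | n | k | 1 − f |
|---|---|---|---|
| PART-1, all periods run, ritonavir in Periods 3 and 4 | 8 | 1 to 4 | 87.5% to 50% |
| PART-1, Periods 1 and 2 only | 4 | 0 | no mixing |
| PART-2, four non-Japanese cohorts | 4 | 1 to 2 | 75% to 50% |
| PART-2, two non-optional cohorts only | 2 | 0 | no mixing |
| PART-5 | all boosted | all | 0% |

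In PART-1 the baseline comes after the ritonavir dose at −12h, so R there is only the change after that point. In PART-2 ritonavir starts at 0h on Day 1, so R is the whole effect. The documents give no value for R. Protocol 4.2 describes the 100 mg dose as subtherapeutic.

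**What splitting would cost.** Treat records as independent with standard deviation s. The standard error of a split line relative to the pooled line is √(N pooled / N line).

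- PART-1, 2 of 8 cohort-periods boosted: boosted line √(16/4) = 2.00; unboosted line √(16/12) = 1.15.
- PART-2, 1 of 4 cohorts boosted: boosted line √(8/2) = 2.00; unboosted line √(8/6) = 1.15.

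**When splitting would pay.** Take a line holding a share p of N placebo records. Pooling adds a squared bias of (1 − p)²R². Splitting adds a variance of s²/(Np) − s²/N = s²(1 − p)/(Np). Splitting has the smaller mean squared error only if R/s > 1/√(Np(1 − p)). This is unchanged when p is replaced by 1 − p, so it holds for both lines.

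| Layout | N | p | R/s must exceed |
|---|---|---|---|
| PART-1, 2 of 8 | 16 | 0.25 | 1/√3 = 0.58 |
| PART-1, 4 of 8 | 16 | 0.50 | 1/√4 = 0.50 |
| PART-2, 1 of 4 | 8 | 0.25 | 1/√1.5 = 0.82 |
| PART-2, 2 of 4 | 8 | 0.50 | 1/√2 = 0.71 |

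So a ritonavir effect of at least half a between-record standard deviation is needed before a split line estimates its own group's mean better than the pooled one.

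**Where the plots are used.** SAP 5.1 says "no statistical decision rules will be applied". The criteria in protocol 6.6.1 rest on participant-level abnormalities, adverse events, PK limits and judgement by the study team and investigator. None cites these figures. SAP 6.6.3 and 6.6.4 also require tables by treatment and time of values and changes from baseline, plus maximum-change and categorical summaries by treatment. Under Section 6 these keep the two placebo groups apart.

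**The case for a change.** The best case for a change is that one sentence would settle the matter, that the endpoints are primary, and that the matched placebo was built into the design. Boosted dosing was also not hypothetical by the time of the current SAP: protocol 4.3.3 refers to exposure already observed at 750 mg with ritonavir, though it does not say in which part.

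Part of this stands. The wording is open, and stating the choice would be tidier. The scope is also a little wider than the mean plots, because the individual plots are specified straight after the pooling sentence and might be grouped the same way. Those show each participant's own course, so grouping them averages nothing.

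The rest does not lead to a required edit. The matched comparison stays in the tables, so the figure is not its only source. Splitting by ritonavir alone would not give a fully matched line either: protocol Table 6 includes a fed placebo period, and the PART-5 rationale in protocol 4.2 chose meal times to keep food from affecting QTc. With about 2 placebo records per cell, pooling for a descriptive figure is a fair choice.

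**Conclusion.** No change to the plan is needed. The SAP leaves a presentation detail unstated, and an analyst can settle it sensibly on either reading without altering any conclusion. If the line is mixed, the plotted gap for boosted doses carries 50% to 87.5% of any post-baseline ritonavir effect in PART-1 and 50% to 75% in PART-2. If each part has a single ritonavir status, it carries none, and PART-5 is never affected. These shares assume about 2 placebo records per cell and ritonavir confined to the optional periods and cohorts. Protocol 4.1 allows regimens to be adjusted, so other mixes are possible. The shares cannot be turned into msec or mm Hg, because the documents give no ritonavir effect. Separate lines would be noisier, about twofold in standard error for the smaller group in the layouts worked above with a quarter of the cells boosted. A footnote with the boosted and unboosted placebo counts, added when the figures are made, would tell the reader what is plotted and needs no SAP revision.
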